#### Secondary care

Since 2016, NHS Improvement has required all NHS trusts and foundation trusts to provide a weekly return detailing their use of locum medical staff, particularly high cost locums and adherence to locum pay caps. In addition, the three national procurement framework operators for NHS Improvement (Crown Commercial Services, Commercial Procurement Collaborative and Health Trust Europe) collect detailed information on all locum placements by suppliers registered on the framework through mandatory management information returns. This data has been used to produce some management statistics for NHS Improvement on locum usage/costs but otherwise has not been analysed to date. We have secured support and agreement in principle from NHS Improvement colleagues to us accessing this data, subject to necessary information governance approvals.

As the data are currently used by the NHS we believe the quality to be sufficient for our planned analyses. However, we will first need to undertake work to evaluate data quality and completeness over the period available, assessing the consistency of data definitions and their application and writing and applying code to clean data and check for data errors/inconsistencies. Any issues involving quality or completeness will be fed back to NHS Improvement so the data may be corrected for future releases.

We will then link data to available trust-level characteristics of interest, such as bed availability/occupancy and CQC inspection ratings, as well as using published aggregated Hospital Episode Statistics (HES) data on inpatient and outpatient activity by specialty and month/year. We will produce descriptive analyses of variations in locum usage by specialty, trust type and geographic area over time. We will use regression analysis (mirroring the approach described for primary care) to examine associations between locum usage and specialty/trust characteristics.

### WP4: Collection and analysis of existing/routine quantitative data sets to compare locum and permanent doctor practice/performance in primary and secondary care (RQ3)

Most routine/existing NHS datasets do not contain sufficient information to distinguish reliably between care provided by locum and non-locum doctors, and so our approach to quantitative analysis makes careful and informed use of selected datasets in which our pilot work has established this analysis is feasible, in order to address RQ3. Locum doctors can be identified either where the staff role is explicitly coded in the data set as a locum, or where records contain medical staff identifiers which can be linked to staffing/HR databases. However, especially in team settings where care may be provided by a number of medical staff including both locums and permanent doctors, it is difficult both to identify and to distinguish the distinctive contribution of locum doctors. For example, an activity (such as admission, discharge, test ordering, prescribing, operative procedure, etc) may be recorded by one member of a team (whether a locum or permanent doctor) but may have been initiated by another.

For this reason, out our quantitative analyses will focus primarily on primary care, where the quality of data is high, locum information is known to be reliably collected and available in CPRD, and the attribution of activities to individual doctors (whether permanent or locum) is less problematic. However, we also set out plans for a more limited feasibility study in

secondary care, using Electronic Patient Record (EPR) data from one NHS trust with the capacity to extend the analysis to others.

#### **Primary care**

We will use the Clinical Practice Research Datalink (CPRD) to access electronic health records (EHRs) from primary care practices. The database holds anonymised general practice records on all registered patients, including diagnoses, test, prescribed treatments and referrals. Each interaction with a health professional is recorded, through unique identifiers for patients, consultations and health professionals. The staff role field can be used reliably to identify the type of GP (partner, salaried, or locum) involved in any recorded interaction. In addition, linkage to Hospital Episodes Statistics (HES) data is available. This allows us to obtain detailed information on any form of hospital attendance for all patients in the practices that are part of this linkage scheme. Our proposal plans to use data from both CPRD Gold (practices using Vision software) and the more recent CPRD Aurum (practices using EMIS). In total we should be able to access data from about 1,100 practices for a median period of 10 years, involving millions of patient, the great majority of which have given permission for the practice data to be linked to HES.

We will analyse the data in bins of financial years. Within each financial year, our population will comprise of patients registered with a CPRD general practice for whole of the year. Preliminary analyses in CPRD have confirmed that the available staff role identifier is widely and reliably used across practices, and we will use it to identify locum and permanent GPs. This will be our key parameter of interest and we will evaluate its association with important patient outcomes. All analyses will be conducted at the patient level.

We will focus on service utilisation and patient outcomes. Our primary outcomes will be patients revisiting the general practice within 7 days or 15 days. Secondary outcomes will include: referrals to secondary care, unplanned hospital admissions within 7 days or 15 days (through HES linkage), A&E attendance within 7 days or 15 days (through HES linkage), ambulatory care sensitive conditions (ACSC) hospitalisations within 7 days or 15 days (through HES linkage), antibiotic prescriptions, and validated prescribing safety indicators (as established measures of clinical performance and quality of care) which we have already used in a prior study using the CPRD.(44)

All analyses will be controlled for available patient, general practitioner and general practice characteristics. Patient: age, sex, deprivation as measured by the 2015 Index of Multiple Deprivation (IMD, in quintiles),(45) years registered with the practice (if not collinear with age), number of practice visits in the previous financial year (or in the previous 12 months since the current consultation event) and numerous chronic conditions which are well recorded in these databases since they are part of the Quality and Outcomes Framework (atrial fibrillation, asthma, cancer, coronary heart disease, chronic kidney disease, chronic obstructive pulmonary disease, dementia, depression, diabetes, epilepsy, heart failure, hypertension, limiting disabilities, severe mental health, osteoporosis, peripheral arterial disease, rheumatoid arthritis and stroke).(46) General practitioner: sex/age are unavailable, but see analytical plan below). General practice: list-size, urban/rural location, practice location IMD (in quintiles), region, ratio of locum consultations over total within the

respective analysis year. We will also derive and describe consultation characteristics, like type, length and day of the week, although these will be used for descriptive purposes.

Our power calculation is based on the primary outcome, revisiting general practice within 7 days, and on the assumption that 10% of patients consulting a permanent GP return within that time period. Assuming 9 consultations with a permanent GP for 1 consultation with a locum, an alpha level of 5%, and an increase in the outcome to 15% for locum consultations (OR=1.59), we would need a total of 4330 patients to have 90% power to detect the association. Although this approach ignores between-practice variability in both the intercept and the association (e.g. varying return rates for permanent GPs and locus), it does demonstrate that we have many hundreds (if not thousands) times the numbers needed to detect a meaningful association.

All outcomes and key covariates of interest will be appropriately described over time, at the patient, GP and general practice level. For example, we will plot the percentage of revisits within 7 days by locum/permanent GP groups, across all practices, over time. We will use multi-level mixed effects logistic regression models to quantify the association between the exposure of interest (locum/permanent GP) and the outcomes of interest, controlling for all available covariates previously discussed. If an outcome (e.g. safety indicators) in better expressed as a count, e.g. if we identify that numerous indicators tend to apply to visits, we will use multi-level mixed effects Poisson or negative binomial regression models instead. Analyses will be conducted at the patient level, accounting for the nested structure of the data: patients within general practices, within regions. We will include random effects for practices and possibly for regions (alternatively a fixed effect for regions).

We will use two designs to reliably evaluate the association of interest. Within each financial year, we will randomly select one consultation for each patient, and then align all the outcomes and covariates to that specific event date for the patient. This will allow us to give equal weights to patients, and limit the potential for confounding introduced by patients with very poor health who may be visiting numerous times within a year. The first design, will involve a multi-level regression on all randomly selected consultation events, which will be used to obtain adjusted estimates for the exposure of interest. The second design will involve an additional step before the regression analysis, propensity score matching. This approach will attempt to select two patient samples for each exposure group (locum/permanent GP) that are as "close" and comparable as possible, in terms of all their available characteristics. We will use logistic regression to obtain the propensity score for each patient within a financial year, the probability of membership to each exposure group (locum/permanent GP) given the observed covariate values. The score will then be used to match patients in the two groups of interest, using their propensity scores (10 in the permanent GP group to 1 in the locum group – with no replacements). The propensity scores will be plotted over time and the performance of the matching process will be evaluated. Next, the matched sub-samples will be analysed with the multi-level regression models previously described. Our primary analyses will be the unmatched regressions, since our group has conducted methodological work that has demonstrated that matching can be detrimental in large samples (the methods work well for small and very small samples), while the recommended conditional regression approach for matched samples does not

confer any benefits (while it's less flexible when it comes to modelling the nested structure of the data).

Data will be complete (e.g. a patient either is coded as having diabetes or not) and of high quality since tied to financial incentives (e.g. QOF) or almost impossible not to record (e.g. consultation, or prescribing). Therefore, we will not need to use a multiple imputation framework or anything similar. Confounding is a concern, with urgent requests perhaps being more likely handled by locums – e.g. a patient cannot afford to wait for 2 weeks before his/her regular GP is back from holiday. We will partly attempt to control for that through the available patient characteristics, but we will also interpret our results with caution and use the recently suggested E-Value to assess the potential effect of unmeasured confounding.(47) The age of GPs is not available in the database, and another concern is that locums may be much less experienced that permanent GPs, hence any potential differences could be attributed to that rather than the locum status. Although we need to be careful not to "overcontrol" the analyses for the characteristics of locum GPs, since numerous GPs close to or in retirement choose to locum, we will conduct a sensitivity analysis where we will exclude more experienced permanent GPs (thus focusing on GP registrars, salaried GPs and GP retainers vs locums, repeating all analyses previously described).

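### WP4 primary care names two primary revisit windows in one place and one in another, and its model lists no financial-year term and no allowance for patients who recur across years

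*Protocol*

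**What the plan says.** All references are to Protocol section 5, WP4, Primary care, unless stated.

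- **Time unit and data.** "We will analyse the data in bins of financial years". The study population is defined within each year, and "In total we should be able to access data from about 1,100 practices for a median period of 10 years".
- **Sampling.** "Within each financial year, we will randomly select one consultation for each patient". The propensity score for the matched design is also built within a year.
- **Model.** A mixed-effects logistic regression treats patients as nested in practices and practices in regions: "We will include random effects for practices and possibly for regions". The first design applies it to all the randomly drawn consultations. The covariate list covers patient and practice characteristics, including each practice's share of locum consultations in the analysis year. It contains no financial-year term.
- **Primary analysis.** "Our primary analyses will be the unmatched regressions". This settles unmatched against matched and nothing else.
- **Primary outcome.** "Our primary outcomes will be patients revisiting the general practice within 7 days or 15 days". The sample-size paragraph reads differently: "Our power calculation is based on the primary outcome, revisiting general practice within 7 days", at "an alpha level of 5" per cent.
- **Background (section 2).** The number of locums in primary care is reported to have risen by 250% between 2015 and 2019.

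**The concern.** Two things in the text need correcting.

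First, the number of primary outcomes is stated inconsistently: two in the outcome paragraph, one in the power paragraph. A reader cannot tell whether a difference at 15 days alone would answer research question 3.

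Second, sampling is by year but the model is described without years. Each way of resolving this leaves a gap.

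- **One pooled fit.** Locum use rose over the period, so any drift in revisit rates over calendar time can pass into the locum contrast. A patient who consults in ten years supplies ten rows, yet the nesting stops at patients within practices, so those rows count as independent given the practice. Patients who consult in more years also carry more weight, although equal weighting was a stated reason for the yearly draw.
- **Separate yearly fits.** There is no rule for turning about 10 odds ratios per window into one answer.

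WP4 is the only work package assigned to research question 3, and its quantitative work centres on primary care. The choice of deciding estimate should therefore be closed before results are seen.

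**Working it through.** **1. The plan's own figures.** Planning odds ratio: (0.15/0.85)/(0.10/0.90) = 1.588, stated as 1.59. The stated total of 4330 is approached by a two-sided Wald calculation on the log odds ratio at 90% power and 9:1: 10 × (1.960 + 1.282)² × [1/(0.15 × 0.85) + 1/(9 × 0.10 × 0.90)] / (ln 1.59)² = 4435. The usual two-proportion formula gives 4920. The available data far exceed either figure, so sample size is not at issue. The calculation matters here because it uses one outcome and one test at 5%.

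**2. Two windows in one pooled model.** A 7-day revisit is also a 15-day revisit, so the two tests correlate at about √[p7(1 − p15)/(p15(1 − p7))]. With p7 = 0.10 (protocol) and p15 assumed between 0.14 and 0.25, the correlation is 0.83 to 0.58. By simulation, the chance that at least one two-sided 5% test is falsely positive is 0.076 to 0.088. The ceiling under independence is 1 − 0.95² = 0.0975.

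**3. Calendar time in a pooled fit without a year term.** Assumptions: ten equal years, no true locum effect, locum share rising linearly from 5% to 15% (mean 10%, matching the protocol's 9:1), and revisit rate rising linearly around a mean of 10%. Ten equally spaced points on a unit range have variance 11/108 = 0.1019.

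- Rise of 1 point (9.5% to 10.5%): covariance of share and rate = 0.10 × 0.01 × 0.1019 = 0.000102. Locum rate = 0.10 + 0.000102/0.10 = 0.1010; permanent rate = 0.10 − 0.000102/0.90 = 0.0999; odds ratio 1.013.
- Rise of 3 points (8.5% to 11.5%): covariance 0.000306; rates 0.1031 and 0.0997; odds ratio 1.038.

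With an assumed 5 million rows, the standard error of the log odds ratio is √[1/(5,000,000 × 0.1 × 0.9 × 0.1 × 0.9)] = 0.0050, so these biases are about 2.5 and 7.5 standard errors. They are upper figures. The planned practice-by-year locum ratio also rises over time. If it enters linearly and equals the locum share among the selected consultations, the locum term becomes a contrast within practice and year, and this bias vanishes. If it tracks that share imperfectly, part of the bias remains.

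**4. Repeated patients in a pooled fit.** With m rows per patient, the variance of the locum coefficient grows by about 1 + (m − 1) × ρx × ρy, where ρx and ρy are the between-year correlations of exposure and of outcome within a patient, beyond the practice effect. Take m = 10 and both correlations between 0 and 0.2 (assumed). The factor runs from 1 to 1 + 9 × 0.04 = 1.36, so the true standard error is 0 to 17% larger than the one reported. At 17%, a nominal 5% test rejects when |z| > 1.96/1.166 = 1.68, which is about 9%.

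**5. Separate yearly fits.** Ten tests of one window: 1 − 0.95^10 = 0.40 if years are independent, and 0.29 (simulated) at a between-year correlation of 0.5. Ten years by two windows: 0.61 (year correlation 0, window 0.5), 0.55 (0.2, 0.7) and 0.44 (0.5, 0.7); simulation error puts the last at 0.43 to 0.44.

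**The case against.** A reader might infer that about 20 odds ratios, ten years by two windows, could each be called the primary result at 5%. The protocol does not support that. The yearly restriction is attached to the consultation draw, whereas the regression is described in the singular and over all drawn consultations, which leans towards one pooled fit. WP3 speaks of time bins inside a panel model, so bins need not mean separate fits. The plural in the primary-analysis sentence is explained by several outcomes. The power paragraph already treats 7-day revisit as the one primary outcome, and no sentence lets a single year decide. The ten years is a median per practice, not a count of analysis years.

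Family-wise error is also a blunt measure here. The 5% level appears only in the power calculation, and the protocol promises cautious interpretation and an E-value. Assuming 200,000 to 1,000,000 patients a year, 10% with locums and 10% revisiting, the yearly standard error is about 0.025 to 0.011. A chance finding would then be an odds ratio of only about 1.05 to 1.02, against the planning value of 1.59.

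Finally, year terms, robust standard errors and multiplicity rules often sit in a statistical analysis plan, which is not at hand. All of this stands as a limit on size. It does not remove the conflict over the number of primary outcomes. Nor does it change that the protocol itself lists the covariates and the nesting, and both are incomplete for a pooled fit.

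**Conclusion.** The point holds in a moderate form. The inconsistency between two primary windows and one is certain from the text and is worth about 0.08 instead of 0.05 under a pooled fit. On the pooled reading, which the text favours, the listed model has no year term and no allowance for recurring patients. The possible bias is an odds ratio of at most about 1.01 to 1.04 under assumed trends, and smaller or nil to the extent that the locum-ratio covariate absorbs them. Standard errors would be 0 to 17% too small under assumed correlations. Neither could produce an effect near 1.59, but in a data set this large either could make a trivial difference look established. On the yearly reading, the rule for combining years is missing and the family-wise rate for one window is 0.29 to 0.40. The 0.43 to 0.61 for both windows is a worst case that takes the less favourable reading of both ambiguities, and should not be presented as the plan's error rate.

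**What to change.** In the WP4 Primary care section:

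1. In the outcome paragraph, make revisit within 7 days the single primary outcome, as the power calculation already does, and list 15-day revisit as secondary.
2. In the paragraph on the two designs, state that the locum versus permanent odds ratio comes from one unmatched model pooled over all financial years, with financial-year indicators added to the covariates.
3. In the same paragraph, state that standard errors are robust to repeated patients within practice. A patient random effect is not needed: with millions of patients it is demanding to fit, and it changes the odds ratio to a patient-conditional one.
4. Report year-specific odds ratios as description, with one locum-by-year interaction test.

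The cost is a few sentences and a somewhat heavier fit. Data and extraction do not change. The price is that no single-year or 15-day result can be presented as the main finding.

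### Requiring registration for the whole financial year makes entry to the WP4 primary care cohort depend on events after the index consultation, and does not secure the 12-month look-back

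*Protocol*

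**What the plan says.** All of this is in the Protocol, Section 5, WP4, Primary care.

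- Time unit: "We will analyse the data in bins of financial years".
- Population within each year: "our population will comprise of patients registered with a CPRD general practice for whole of the year".
- Index event: "Within each financial year, we will randomly select one consultation for each patient". The plan is then to "align all the outcomes and covariates to that specific event date for the patient".
- Outcomes: "Our primary outcomes will be patients revisiting the general practice within 7 days or 15 days". Secondary outcomes include "unplanned hospital admissions within 7 days or 15 days (through HES linkage"), with the same windows for A&E attendance and for hospitalisation for ambulatory care sensitive conditions (ACSC).
- Look-back covariate: "number of practice visits in the previous financial year (or in the previous 12 months since the current consultation event").
- Length of registration is an adjustment variable only: "years registered with the practice (if not collinear with age").

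The section gives no rule for patients who die or leave the practice after the index consultation, and requires no registration before the current financial year. It describes the data as complete. It also anticipates that locums may see more of the urgent requests.

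**The concern.** Exposure is fixed at the index consultation, but eligibility is settled only on 31 March. Read literally, someone who sees a GP in June, is admitted within a week and dies or moves away in the autumn was not registered for the whole year. Both the patient and the admission leave the analysis. That is selection on events after exposure.

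The planned safeguards do not address it. Regression adjustment and propensity matching use baseline characteristics. The E-value concerns unmeasured confounding. The random choice of consultation operates only among patients already selected. The very large sample reduces random error, not this one.

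The look-back has the opposite problem. The prior-visits covariate needs up to a year of record before the index date, and the rule guarantees none before 1 April. A recent joiner can appear to be a low user simply because the practice holds no earlier record, which weakens adjustment for previous use.

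**Working it through.** **1. The plan's own figure.** The only design figure for this analysis is the total of 4330 patients. A two-sided Wald calculation on the log odds ratio gives (1.960 + 1.282)² × [1/(0.1×0.15×0.85) + 1/(0.9×0.10×0.90)] / (ln 1.588)² = 4457, which is 2.9% above it. The registration rule does not enter this calculation, and the figure is not in dispute here.

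**2. Registration required after the index date.** An index on day d of a 365-day year is kept only if registration continues for 365 − d more days. That is 0 to 364 days, with a mean of about 182 if index dates are uniform (assumed). The outcomes need 7 or 15.

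**3. When this biases the comparison.** Let s be the probability of remaining to 31 March, by group (L locum, P permanent) and outcome (1 yes, 0 no). Then

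OR in the kept cohort = OR in all patients × (s_L1 / s_L0) / (s_P1 / s_P0).

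If retention is the same in both groups at each level of the outcome, the factor is 1 and the odds ratio is unbiased. Bias needs retention to depend on group and outcome jointly.

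**4. Illustration for admission (all inputs assumed).** Take 7-day admission of 1.8% (locum) and 1.5% (permanent), a true ratio of 1.20. Let f be the share of admitted patients lost before 31 March, with f_P = 15%. Assume loss among the non-admitted is equal in the two groups, and ignore the small change in denominators. Analysed ratio = 1.8(1 − f_L) / [1.5(1 − f_P)]:

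| f_L | Calculation | Analysed ratio |
|---|---|---|
| 15% | 1.530/1.275 | 1.20 |
| 16.5% | 1.503/1.275 | 1.18 |
| 20% | 1.440/1.275 | 1.13 |
| 25% | 1.350/1.275 | 1.06 |

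The last two rows are strong assumptions. They put loss after admission at 0.36% and 0.45% of locum patients against 0.225% of permanent-GP patients, which is 1.6 and 2.0 times as much.

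**5. Illustration for 7-day revisit (all inputs assumed).** Suppose kept patients revisit at 10% in both groups (OR 1.00), the rule removes 5% to 15% of permanent-GP patients and 1.5 times that share of locum patients, and removed patients revisit at 2 to 3 times the base rate.

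- Low end: permanent 0.95×10% + 0.05×20% = 10.5%; locum 0.925×10% + 0.075×20% = 10.75%; full-cohort OR 1.03.
- High end: permanent 0.85×10% + 0.15×30% = 13.0%; locum 0.775×10% + 0.225×30% = 14.5%; full-cohort OR 1.14.

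With equal removal, or equal revisit risk in those removed, the full-cohort OR is 1.00.

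**6. Look-back.** Registration guaranteed before the index date is only the time since 1 April: 0 to 364 days, about 182 on average under uniform dates. For the previous-financial-year version of the covariate it is 0 days. A patient who joined on 1 April qualifies with no earlier record at that practice.

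**7. Year end.** Index dates in the last 7 or 15 days of March make up 7/365 = 1.9% or 15/365 = 4.1% of uniform dates. The section does not stop outcome follow-up at 31 March, so these are shares of dates, not of lost follow-up. If 5% to 15% of patients leave or die per year (assumed), the share with a window cut short in April is about 1.9% × (4/365) × 5% to 15% = 0.001% to 0.003% for 7 days, and 4.1% × (8/365) × 5% to 15% = 0.005% to 0.014% for 15 days. The 4 and 8 are the mean days running past year end. This is negligible.

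**The case against.** Full-year registration gives a stable denominator for annual bins and largely avoids unobservable revisits in patients who have left. The protocol claims associations only and promises cautious interpretation. Death is not a primary care outcome in WP4; mortality appears only in the secondary care feasibility study. Admitted patients who survive and stay registered are kept, so the rule selects on survival and registration, not directly on the outcome. The one mortality comparison the protocol reports, a US inpatient study described in Section 2 and so only indirect, found no significant overall difference between locum and permanent physicians, though mortality was higher with locums in hospitals that used them infrequently. Nothing in the protocol supports the larger differences in step 4. On the look-back, the 12-month option is already offered, years registered helps to identify recent joiners, and a minimum prior registration is detail that a statistical analysis plan may settle.

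Most of this stands, and it limits the point. It does not remove it, because the full-year rule is stated, not left open, and it feeds every WP4 primary care outcome in both the regression and the matched design. Years registered offsets the truncated visit count only in part, and is kept only if it is not collinear with age.

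Three stronger readings are tempting and unsupported. A reader might infer that anyone who dies or leaves after the consultation is excluded; only those who do so before 31 March of the same financial year are. A reader might infer that follow-up is lost for late-March consultations; step 7 shows otherwise. A reader might infer that the rule hides harm from locum care; that needs differential loss, for which the protocol gives no figures.

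**Conclusion.** The point holds as a design weakness of unknown size. Eligibility conditions on survival and continued registration for up to 364 days after exposure when 7 or 15 would do. This can bias the locum/permanent comparison, most plausibly for admission, A&E and ACSC outcomes. The protocol's own expectation about urgent requests makes differential loss possible but does not show it. Size and direction cannot be determined from the document, and the ratios in steps 4 and 5 show only what particular assumptions would produce. The look-back gap is real but secondary. The rule is worth changing before data extraction; the material does not support calling the comparison invalid as planned.

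**What to change.** - Define eligibility at the index consultation: registered for at least the preceding 12 months, with no requirement to remain registered to year end. Apply this before the random draw, so that the draw is made among eligible consultations.
- Use only the version of prior visits that covers the 12 months before the index date.
- State a simple rule for death or deregistration inside the 7- or 15-day window. For example, keep such patients in the denominator with outcomes observed to that point, and add a sensitivity analysis counting death as an event. This stays within the planned logistic models.
- Report the full-year cohort as a sensitivity analysis, which would show how much the rule matters.

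The cost is a change in wording and cohort code, with no new data source. Patients registered for under 12 months are lost. A small number of retained patients will have incomplete windows: at an assumed constant 5% to 15% leaving or dying per year, (7/365) × 5% to 15% = 0.1% to 0.3% for 7 days and (15/365) × 5% to 15% = 0.2% to 0.6% for 15 days.
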